Subjects in dose expansion may have received up to 2 prior endocrine therapies and up to 1 prior chemotherapy regimen but may not have received a prior CDK4/6 inhibitor in the advanced or metastatic setting.

Subjects who are tolerating therapy and are without progressive disease may receive treatment until progression.

Dose escalation will determine the MTD and/or the RP2D of H3B-6545 in combination with palbociclib. Due to the potential for screen failures and/or a subject discontinuing treatment before completion of the cohort DLT assessment window (non-evaluable for DLT assessment), up to 8 slots will be opened for screening in order to obtain 6 DLT-evaluable subjects (See Section 9.1). In addition, subjects considered screen failures or unevaluable for DLT will be replaced. Each cohort will consist of 6 DLT-evaluable subjects to ensure sufficient safety and PK data are obtained prior to dose escalation. A cycle of treatment will be 28 days.

In the 1st cycle, palbociclib will be administered orally (PO) once daily (QD) on Days 1 to 21 and H3B-6545 will be administered PO QD on Days 9 to 28. In all subsequent cycles, palbociclib will be administered on Days 1 to 21 and H3B-6545 will be administered Days 1 to 28.

A maximum of 4 dose levels are planned, with palbociclib escalated no higher than 125 mg QD and H3B-6545 escalated no higher than 450 mg QD (RP2D).

Dose Level (Cohort)	Palbociclib Dose (mg QD)	H3B-6545 Dose (mg QD)	Number of DLT- Evaluable Subjects
-1	75	300	6
1 (starting dose)	100	300	6
2	125	300	6
3	125	450	6
3b	100	450	6

Dose Escalation Table

DLT= dose-limiting toxicity; QD = once daily.

Subjects will be assigned to a dose level in the order of study entry.

Dose-limiting toxicities (DLTs) will be assessed during the first 28 days starting from the 1st day of adding H3B-6545 to palbociclib (Cycle 1 Day 9 to Cycle 2 Day 8). Subjects who do not receive at least 75% of the scheduled therapy from Cycle 1 Day 9 to Cycle 2 Day 8, for

reasons other than toxicity, will not be considered evaluable for DLT assessment and will be replaced. Disease progression and adverse events (AEs) deemed related to disease progression will not be considered DLTs.

After 6 DLT-evaluable subjects in a cohort have completed the DLT observation period, all available safety data will be reviewed by the Safety Review Committee (SRC) consisting of sponsor personnel and investigators.

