- **Cohort 1:** If none or only 1 subject experienced a DLT, initiate enrollment in Cohort 2. If 2 or more subjects experienced a DLT, initiate enrollment in Cohort -1.
- **Cohort -1:** If none or only 1 subject experienced a DLT, the doses used in Cohort -1 will be considered the RP2D. If 2 or more subjects experienced a DLT, the combination of H3B-6545 and palbociclib at clinically meaningful doses will be considered unfeasible.
- **Cohort 2:** If none or only 1 subject experienced a DLT, initiate enrollment in Cohort 3. If 2 or more subjects experienced a DLT, the doses used in Cohort 1 will be considered the MTD and the RP2D.
- **Cohort 3:** If none or only 1 subject experienced a DLT, doses used in this Cohort will be considered the RP2D. If 2 or more subjects experienced a DLT, consideration will be given to opening cohort 3b depending upon observed toxicity profile.
- **Cohort 3b:** If none or only 1 subject experienced a DLT, doses used in this Cohort and in Cohort 2 could be considered the RP2D. In this case, the SRC will select between Cohort 2 and Cohort 3b for the expansion phase. If 2 or more subjects experienced a DLT, doses used in Cohort 2 will be considered the RP2D.

The MTD is defined as the highest dose at which no more than 1 of 6 subjects experiences a DLT in the dose cohort. The RP2D may not exceed the MTD and will be agreed upon by the SRC based on an integrated evaluation of available safety, clinical benefit, PK, and pharmacodynamics data, for all dose levels tested.

DLTs: Unless considered not related to study drugs, any of the following criteria will qualify as a DLT:

Toxicity	Criteria ^a	
Hematology	- Febrile neutropenia (ANC <1×10 ⁹ /L and fever \ge 38.5 ° C)	
	- Grade 4 neutropenia that does not resolve to Grade ≤ 2 (ANC $\geq 1 \times 10^{9}/L$) within 7 days; use of GM-CSF is allowed	
	- Grade 4 thrombocytopenia (<25.0×10 ⁹ /L)	
	 Grade 3 thrombocytopenia (25.0 – 50.0×10⁹/L) lasting more than 7 days or associated with clinically significant bleeding 	
Vomiting	- CTCAE Grade 4 vomiting	
	- Grade 3 vomiting lasting >72 hours despite optimal antiemetic treatment	
Diarrhea	- CTCAE Grade 4 diarrhea	
	- Grade 3 diarrhea lasting >72 hours despite optimal antidiarrheal treatment	

Electrolytes abnormality	 Grade 4 Grade 3 lasting for more than 24 hours Note: Grade 3 that lasts <24 hours and resolves spontaneously or responds to conventional medical interventions is not considered a DLT. 	
Renal	- Grade 3 or 4 serum creatinine	

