- The current cohort so that the total number of DLT-evaluable subjects is maintained at 6, if any of the 6 already dosed subjects becomes non-evaluable for DLT;
- A lower dose cohort which has already been deemed safe per dose escalation meeting, if none of the 6 already dosed subjects becomes non-evaluable for DLT in the cohort currently under evaluation; the additional subject(s) will not contribute to DLT evaluation of the lower dose cohort, but will contribute to the overall safety evaluation.
- The next cohort to be opened to enrollment including the expansion cohort if the RP2D has been reached and the expansion phase is open to enrollment.

Sponsor approval of any enrollment scenario not described above must take place prior to screened subject enrollment.

In the 1st cycle, palbociclib will be administered PO QD on Days 1 to 21 and H3B-6545 will be administered PO QD on Days 9 to 28. In all subsequent cycles, palbociclib will be administered on Days 1 to 21 and H3B-6545 will be administered Days 1 to 28.

A maximum of 4 dose levels are planned, with palbociclib escalated no higher than 125 mg QD and H3B-6545 escalated no higher than 450 mg QD (RP2D); see dose escalation in Table 3.

Dose Level (Cohort)	Palbociclib Dose (mg QD)	H3B-6545 Dose (mg QD)	Number of DLT- Evaluable Subjects
-1	75	300	6
1 (starting dose)	100	300	6
2	125	300	6
3	125	450	6
3b	100	450	6

Table 3Dose Escalation

DLT = dose limiting toxicity; QD = once daily.

Subjects will be assigned to a dose level in the order of study entry. DLTs will be assessed during the first 28 days starting from the 1st day of adding H3B-6545 to palbociclib (Cycle 1 Day 9 to Cycle 2 Day 8). Subjects who do not receive at least 75% of the scheduled therapy

from Cycle 1 Day 9 to Cycle 2 Day 8, for reasons other than toxicity, will not be considered evaluable for DLT assessment and will be replaced. Disease progression and AEs deemed related to disease progression will not be considered DLTs.

After all subjects in a cohort have completed the DLT observation period, all available safety data will be reviewed by the Safety Review Committee (SRC) consisting of sponsor personnel and investigators, and the decision to proceed to the next dose cohort will be made jointly.

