Dose escalation will proceed if <2 of 6 evaluable subjects experience a DLT and will continue until a dose level where ≥ 2 of 6 subjects experience a DLT. If ≥ 2 of 6 subjects in the starting dose cohort experience a DLT during the first cycle, then the dose level -1 will be explored.

The MTD is defined as the highest dose at which no more than 1 of 6 subjects experiences a DLT in the dose cohort. The RP2D may not exceed the MTD and will be agreed upon by the SRC based on an integrated evaluation of available safety, clinical benefit, PK, and pharmacodynamics (PD) data, for all dose levels tested.

DLT is based on the National Cancer Institute (NCI) Common Terminology Criteria for Adverse Events (CTCAE). DLT refers to toxicities experienced by subjects enrolled to the dose escalation portion of the trial during the first 2 cycles of treatment, which are at least possibly related to the study drug. A DLT will be defined as indicated in Table 4.

Toxicity	Criteria ^a		
Hematology	- Febrile neutropenia (ANC $<1\times10^{9}/L$ and fever ≥38.5 ° C)		
	- Grade 4 neutropenia that does not resolve to Grade ≤ 2 (ANC $\geq 1 \times 10^{9}/L$) within 7 days; use of GM-CSF is allowed		
	- Grade 4 thrombocytopenia (<25.0×10 ⁹ /L)		
	 Grade 3 thrombocytopenia (25.0 – 50.0×10⁹/L) lasting more than 7 days or associated with clinically significant bleeding 		
Vomiting	- CTCAE Grade 4 vomiting		
	- Grade 3 vomiting lasting >72 hours despite optimal antiemetic treatment		
Diarrhea	- CTCAE Grade 4 diarrhea		
	- Grade 3 diarrhea lasting >72 hours despite optimal antidiarrheal treatment		
Electrolytes abnormality	 Grade 4 Grade 3 lasting for more than 24 hours Note: Grade 3 that lasts <24 hours and resolves spontaneously or responds to conventional medical interventions is not considered a DLT. 		
Renal	- Grade 3 or 4 serum creatinine		
Hepatic	- Grade 3 or 4 bilirubin increase		
	- ALT or AST $> 8 \times ULN$		

Table 4 Definition of Dose-Limiting Toxicity

	- In absence of liver metastases at baseline and in absence of clinical or radiological evidence of biliary obstruction: ALT or AST >3 × ULN, in conjunction with total bilirubin >2 ×ULN
Biochemistry	 Grade 4 Grade 3 lasting more than 7 days, unless considered not clinically significant as per the discretion of the investigator

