9.4.7.3 Permitted Concomitant Medications

No routine prophylactic antiemetic is required. However, the use of palonosetron, prochlorperazine, promethazine, and cyclizine for management of nausea and vomiting is allowed. The use of ondansetron and granisetron is not permitted because of their potential to prolong QT interval.

Medications may be administered for maintenance of existing conditions prior to study enrollment or for a new condition that develops while on study, including but not limited to the following:

- Growth factors: Prophylactic use of GCSF is not allowed from Cycle 1 Day 9 to Cycle 2 Day 8. Subjects receiving recombinant erythropoietin or darbepoietin-α prior to study start may continue to receive pretreatment doses. Following initiation of study treatment, the use of erythropoietic and granulocyte growth factors in accordance with local practice or ASCO guidelines may be implemented at the discretion of the treating physician.
- Bisphosphonate use, as recommended according to practice guidelines as long as the subject has been on a stable dose for >30 days prior to study enrollment
- RANKL inhibitor use, as recommended according to practice guidelines, as long as the subject has been on a stable dose >30 days prior to study enrollment
- Anticoagulation with warfarin and derivatives will not be permitted. Should a thrombotic event occur while the subject is receiving treatment, the subject may continue, but low-molecular-weight heparin, dabigatran, or edoxaban will be the preferred treatment.
- Subjects who develop hyperglycemia during the study should be treated as determined by the treating clinician, according to the national diabetes management guidelines.

Other medications considered necessary for the subject's safety and well-being may be given at the discretion of the investigator with the exception of those listed in Section 9.4.7.2.

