Grade 3	 Day 1 of cycle: Withhold drug, repeat complete blood cell count monitoring within 1 week. When recovered to Grade ≤2, start the next cycle at the same dose. Day 15 of first 2 cycles: Continue palbociclib at current dose to complete cycle and repeat complete blood cell count on Day 22. 	Withhold dose until recovery to Grade ≤2; resume drug at next lower dose
Grade 1 or 2	No dose adjustment is required	No dose adjustment is required
All other hematological toxicity		
Grade 4	Withhold dose until recovery to Grade ≤2; resume drug at next lower dose	No dose adjustment is required.
Grade 3	• Day 1 of cycle: Withhold drug, repeat complete blood cell count monitoring within 1 week. When recovered to Grade ≤2, start the next cycle at the same dose.	No dose adjustment is required.

Table 5Dose Modifications and Management Recommendation –Hematologic Toxicities
	• Day 15 of first 2 cycles: Continue palbociclib at current dose to complete cycle and repeat complete blood cell count on Day 22.	
Grade 1 or 2	No dose adjustment is required	No dose adjustment is required
Grade 3 neutropenia with fever ≥38.5 °C and/or infection	Withhold palbociclib until recovery to Grade ≤ 2 ; resume at the next lower dose	Withhold dose until fever subsides; resume at the same dose

CTCAE = Common Terminology Criteria for Adverse Events.

a. Laboratory values that meet criteria listed in this table should be repeated and confirmed within 24 hours of the initial results being reported.

b. Subjects who do not receive at least 75% of the dose for reasons other than toxicity (eg, withdrawal of consent, physician decision, lost to follow-up, etc.) will not be considered evaluable for DLT

Nonhematologic Toxicities

Table 6Dose Modifications and Management Recommendation –Nonhematologic Toxicities

CTCAE Grade	Palbociclib	H3B-6545
Sinus bradycardia		
Grade 1 (asymptomatic) Heart rate ≥40 bpm	No dose adjustment is required	No dose adjustment is required
Grade 1 (asymptomatic) Heart rate <40 bpm	No dose adjustment is required	First occurrence: Withhold drug until heart rate is ≥50 bpm; resume drug at the same dose level
		Second occurrence: Withhold drug until heart rate is ≥50 bpm; resume drug at the next lower dose
Grade 2 (symptomatic, intervention not indicated; change in medication initiated)	No dose adjustment is required	Withhold drug until (a) symptoms resolve and (b) heart rate is \geq 50 bpm; resume drug at the next lower dose

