aPTT = activated partial thromboplastin time; CBC = complete blood cell (count); cfDNA = circulating free deoxyribonucleic acid; CMP = comprehensive metabolic profile; CR = complete response; CRF = case report form; CRP = C-reactive protein; CT = computed tomography; D = day; ECG = electrocardiogram; ECHO = echocardiogram; ECOG = Eastern Cooperative Oncology Group; EOT = end of treatment; HBV = hepatitis B virus; HCV = hepatitis C virus; INR = international normalized ratio; IV = intravenous; MRI = magnetic resonance imaging; MUGA = multiple-gated acquisition; PET = positron emission

tomography; PK = pharmacokinetics; PT = prothrombin time; QTcF = QT interval corrected for heart rate using Fridericia's formula; $T_4 =$ thyroxine; TSH = thyroid-stimulating hormone.

- a. All subjects will be followed for survival approximately every 3 months for up to 6 months after the last subject receives their first dose of study treatment. Subjects will be followed for adverse events for 28 days after the last treatment administration. Subjects who discontinue 1 of the 2 drugs and continue therapy with the other one are considered *on treatment* until they discontinue the 2nd drug.
- b. With the exception of triplicate 12-lead ECG and cfDNA, other assessments performed during the 7 days prior to Cycle 1 Day 1 should need not be repeated, unless otherwise indicated. On Cycle 1 Day 1, scheduled ECG, vital signs, and laboratory tests should be performed predose.
- c. Cycle 2 Day 1 laboratory values for CBC/CMP, INR/PT/aPTT, and urine testing dipstick, can be drawn on Cycle 1 Day 28, in conjunction with the PK blood draw.
- d. Physical examinations will include measurements of weight and vital signs (resting heart rate, blood pressure, respiratory rate, oral temperature). Height will be recorded at the baseline visit only.

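### Protocol Section 9.1 gives three different periods for counting a DLT, and SAP Section 3.2 repeats one of the two that do not match the dated DLT window

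*Protocol*

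**What the plan says.** **The dated window.** Protocol Section 9.1 has DLTs assessed "during the first 28 days starting from the 1st day of adding H3B-6545 to palbociclib (Cycle 1 Day 9 to Cycle 2 Day 8"). The synopsis gives the same window ("will be assessed during the first 28 days starting from the 1st day of adding H3B-6545 to palbociclib", with the same dates), and so does SAP Section 3.2. Two other rules use the same dates: the 75% dosing rule for DLT evaluability in Section 9.1, and Section 9.4.7.3, which says "Prophylactic use of GCSF is not allowed from Cycle 1 Day 9 to Cycle 2 Day 8".

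**The definition.** Further on in Section 9.1, the paragraph that introduces Table 4 says that DLT refers to "toxicities experienced by subjects enrolled to the dose escalation portion of the trial during the first 2 cycles of treatment", provided they are at least possibly related to study drug.

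**The trigger for dose level -1.** Section 9.1 also says that if at least 2 of 6 "subjects in the starting dose cohort experience a DLT during the first cycle, then the dose level -1 will be explored". SAP Section 3.2 repeats this. The synopsis rule for Cohort 1 names no period: "If 2 or more subjects experienced a DLT, initiate enrollment in Cohort -1".

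All of this is current text. None of it comes only from the amendment log.

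**The concern.** The number of subjects with a DLT out of 6 is the decision rule behind the primary endpoint, the MTD and/or RP2D. Escalation proceeds on fewer than 2 of 6. The MTD is the highest dose with no more than 1 of 6, and the RP2D may not exceed it. Intrasubject escalation relies on the same limit. A rule that turns on the difference between one event and two needs a single counting period.

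The protocol sentence that says what a DLT is and the one that says when DLTs are assessed give different periods, and no text says which prevails. For an event outside the window but inside the first two cycles, the protocol supports both counting it and leaving it out. SAP Section 5.6.2 tabulates DLTs without naming a period, so the final table carries the same ambiguity.

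**Working it through.** **Inputs.** A cycle is 28 days (Protocol 9.1). Cycle 1 starts with the first palbociclib dose (9.1.2). H3B-6545 starts on Cycle 1 Day 9 (9.1). Study day of Cycle *c* Day *d*, on schedule, is 28 × (*c* − 1) + *d*.

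**The plan's own figure.** Cycle 1 Day 9 is day 9. Cycle 2 Day 8 is 28 + 8 = day 36. The length is 36 − 9 + 1 = 28 days, which agrees with the stated 28 days.

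**The three periods.**

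| Period | Source | Study days | Length | Shared with window | Outside window |
|---|---|---|---|---|---|
| Dated window | Protocol 9.1, synopsis, SAP 3.2 | 9–36 | 28 | 28 | 0 |
| First two cycles | Protocol 9.1, DLT definition | 1–56 | 56 | 28 | 8 (days 1–8) + 20 (days 37–56) = 28 |
| First cycle | Protocol 9.1 and SAP 3.2, dose level -1 | 1–28 | 28 | 20 (days 9–28) | 8 (days 1–8) |

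The first cycle also misses the last 8 days of the window (29–36). Days 1–8 are palbociclib alone. Palbociclib is a study drug under Section 9.6.1.4.1, so a toxicity related to it in those days can meet the two-cycle definition.

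**Worked cases, 6 evaluable subjects, one event in each of two subjects.**

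| Events | By the dated window | By the other wording |
|---|---|---|
| C1D20 (day 20) and C2D15 (28 + 15 = day 43) | 1 of 6: escalate | Two cycles: 2 of 6: stop |
| C1D5 (day 5, palbociclib alone) and C1D20 (day 20) | 1 of 6: escalate | Two cycles: 2 of 6: stop |
| Cohort 1: C1D20 (day 20) and C2D5 (28 + 5 = day 33) | 2 of 6: stop; the synopsis opens Cohort -1 | First cycle: 1 of 6, so the dose level -1 condition is not met and that sentence gives no instruction |

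Under the synopsis rules, if the first case arose in Cohort 2, the window count would open Cohort 3 (125 mg with 450 mg). The two-cycle count would make Cohort 1 (100 mg with 300 mg) the MTD and RP2D.

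Day 43 is a plausible place for such an event to appear. Table 8 schedules a blood count and a chemistry panel on Cycle 2 Day 15, after the window has closed.

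**The case against.** The strongest reply is that the operative window is explicit. It is dated in the synopsis, Section 9.1 and SAP Section 3.2, and the evaluability rule and the G-CSF restriction share its dates. The Safety Review Committee meets once the DLT observation period is complete, and Table 4's own intolerable Grade 2 criterion refers to that period. The two-cycle wording contains the window, so it could be an outer frame that the dated rule narrows. The committee also sees all available safety data, so late toxicities are not lost.

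Most of this stands. C1D9 to C2D8 is very probably the intended window, and late events would still be reviewed. But no text ranks the sentences, and the two-cycle sentence is written as a definition. The escalation limit and the MTD are numerical rules on DLT counts, so review of a late event does not settle whether it counts.

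A reader might infer more than the documents support:

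- *That dose level -1 opens only on first-cycle DLTs.* The sentence says if, not only if. For the third case above it is silent beside a clear synopsis rule. Escalation stops either way, so nobody is exposed to a higher dose. This part is the milder one.
- *That Table 4, which SAP Section 3.2 cites, carries the two-cycle period.* It does not. The phrase is in the paragraph that introduces the table, and the SAP does not repeat it.
- *That the chance of a discrepant decision can be calculated.* The documents give no DLT rate, DLT timing or accrual pattern, so any probability would come from assumed values.
- *That a late start to Cycle 2 creates a further conflict.* Table 5 can hold palbociclib on Day 1 of a cycle, but the protocol does not say whether cycle numbering moves with it. That is missing detail, not a contradiction.

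Protocol Figure 1 and the SAP's decision-rule figure are not reproduced in the text available, so what they say about the dose level -1 trigger could not be checked.

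**Conclusion.** Wrong as written. Section 9.1 contradicts itself on the counting period for the primary decision rule, and SAP Section 3.2 carries over one of the two stray phrases. Relative to the 28-day window, the definition adds 28 days (8 before, 20 after), and the dose level -1 sentence drops the last 8 days and adds 8 lead-in days. One Table 4 event on days 1–8 or 37–56, alongside one DLT in the window, is enough to move a cohort between 1 of 6 and 2 of 6. The day counts assume on-schedule dosing with 28-day cycles and rest on nothing else. How often the difference would matter is unknown. The likely cause is leftover wording rather than a disputed design choice, which is why the correction should be uncontroversial.

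**What to change.** **Protocol Section 9.1.** Replace the two-cycle phrase in the DLT definition and the first-cycle phrase in the dose level -1 sentence with the DLT window, Cycle 1 Day 9 to Cycle 2 Day 8. The dose level -1 trigger then agrees with the synopsis rule for Cohort 1.

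**SAP Section 3.2.** Make the same replacement in the dose level -1 sentence.

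**SAP Section 5.6.2.** State that DLTs are counted in that window. In the existing DLT listing, flag any Table 4 event outside it that was, or could have been, counted under the other wording.

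**Cost.** Two phrases in the protocol; one phrase, one sentence and one flag in the SAP. Because the protocol edits touch the DLT definition, they may need regulatory and IRB/IEC submission under Section 11.1. SAP Section 3.2 says that no expansion subjects will be enrolled and ties the data cutoff to the last escalation subject, which suggests that escalation is complete. If so, the SAP edits and the flag are enough, with no effect on subjects or timelines.

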Any other non- hematologic AE	Grade 4 Grade 3 (except diarrhea, rash, nausea, or vomiting lasting ≤72 hours) Any drug-related intolerable Grade 2 toxicity (other than hematological AEs) leading to administration of <75% of the dose during the DLT observation period

AE = adverse event; ALT = alanine aminotransferase; ANC = absolute neutrophil count; AST = aspartate aminotransferase; CTCAE = Common Terminology Criteria for Adverse Events; DLT = dose-limiting toxicity; GM-CSF = granulocyte–macrophage colony-stimulating factor; ULN = upper limit of normal.

a. Laboratory values that meet criteria listed in this table should be repeated and confirmed within 24 hours of the initial results being reported.

Intrasubject dose escalation: Once a subject has completed Cycle 3 at her assigned dose level of drug, intrasubject dose escalation will be allowed. No more than 2 dose escalations are allowed for any subject. Only subjects whose conditions have not progressed on treatment and did not have a dose reduction of either palbociclib or H3B-6545 because of AEs can escalate to the highest dose level that has completed DLT assessment and has been shown to be safe (no more than 1 DLT in 6 subjects). Subjects on the intrasubject dose escalation will *not* be included in the DLT analysis at the higher dose level.

Dose expansion: An additional 12 subjects will be treated at the MTD/RP2D to further characterize safety, tolerability, and PK and to provide preliminary estimates of efficacy. In Cycle 1, subjects will receive palbociclib PO QD on Days 1 to 21 and H3B-6545 PO QD on Days 9 to 28. In all subsequent cycles, palbociclib will be administered on Days 1 through to 21 and H3B-6545 will be administered Days 1 through to 28.

AEs will be managed by treatment interruption, dose reduction, and/or treatment discontinuation in accordance with the dose modification instructions outlined in the protocol. Treatment will continue until disease progression, development of unacceptable toxicity, or withdrawal of consent.

The data cutoff date for the primary analysis will be approximately 6 months after the last subject receives their first dose of study treatment. The end of study will be the last assessment for the last subject (eg, the last assessment for the last subject in the Extension Phase).

An overview of the study design and the decision rules for selection of the RP2D is presented in Figure 1.

Figure 1 Study Design and Selection of the Recommended Phase 2 Dose

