9.5 Dose Modifications

Neutropenia was the most frequently reported adverse reaction in palbociclib clinical trials, with an incidence of 80% to 83%. A Grade \geq 3 decrease in neutrophil counts was reported in 66% of patients receiving palbociclib plus letrozole or fulvestrant. The median time to first episode of any grade neutropenia was 15 days and the median duration of Grade \geq 3 neutropenia was 7 days.

Febrile neutropenia has been reported in 1.8% of patients exposed to palbociclib across studies. Physicians should inform patients to promptly report any episodes of fever.

Management of severe or intolerable adverse reactions may require temporary dose reduction and/or interruption of palbociclib and/or H3B-6545.

Recommendations for dose reduction, interruption or discontinuation of either drug in the management of adverse reactions are summarized in Table 5 (hematologic toxicities) and

 Table 6 (non-hematologic toxicities).
 Clinical judgment of the treating physician should guide the management plan of each patient based on individual benefit/risk assessment.

Two dose reductions of H3B-6545 (450 mg to 300 mg, and then to 150 mg QD) for toxicity will be allowed as per the guidance summarized in Table 5 and Table 6. If persistent toxicity occurs despite 2 dose reductions, the subject will discontinue study treatment.

Two dose reductions for palbociclib (125 mg to 100 mg, and then to 75 mg QD) for toxicity will be allowed (Table 5 and Table 6). If persistent toxicity occurs despite 2 dose reductions, the subject will discontinue study treatment.

Hematologic toxicities

Monitor complete blood cell (CBC) counts prior to the start of palbociclib therapy and at the beginning of each cycle, as well as on Day 15 of the first 2 cycles, and as clinically indicated. For patients who experience a maximum of Grade 1 or 2 neutropenia in the first 6 cycles, monitor CBC counts for subsequent cycles every 3 months, prior to the beginning of a cycle and as clinically indicated.

CTCAE Grade	Palbociclib	H3B-6545
Anemia		
Grade 4	Withhold dose until recovery to Grade ≤2; resume drug at next lower dose	Withhold dose until recovery to Grade ≤2; resume drug at next lower dose

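### Table 5 holds H3B-6545 for febrile Grade 3 neutropenia but, read as written, not for febrile Grade 4; secondarily, Table 4 gives anemia no route to being a DLT

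*Protocol*

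**What the plan says.** **Dose modification.** Table 5 in Protocol 9.5 gives each drug its own instruction. After an anemia block comes a block headed "All other hematological toxicity", and then one row for Grade 3 neutropenia accompanied by fever of at least 38.5 °C and/or infection. In that row H3B-6545 is held until the fever has gone and restarted at the same dose. In the Grade 4 line of the general block, the palbociclib entry is "Withhold dose until recovery to Grade ≤2; resume drug at next lower dose", and the H3B-6545 entry says that no adjustment is needed. The text before the table adds that "Clinical judgment of the treating physician should guide the management plan of each patient". Protocol 9.1 says that adverse events are to be managed in line with these instructions.

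**DLT definition.** Protocol 9.1 states "A DLT will be defined as indicated in Table 4", and the synopsis introduces its copy of the table with "any of the following criteria will qualify as a DLT". The hematology row of Table 4 lists febrile neutropenia (ANC below 1×10⁹/L with fever), prolonged Grade 4 neutropenia, and Grade 4 or complicated Grade 3 thrombocytopenia. The last row is for non-hematologic events, and its dose-loss criterion reads "Any drug-related intolerable Grade 2 toxicity (other than hematological AEs) leading to administration of <75% of the dose during the DLT observation period". DLTs are limited to toxicities "which are at least possibly related to the study drug". Escalation proceeds when fewer than 2 of 6 evaluable subjects have a DLT.

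**The concern.** The febrile row is the main point. Its H3B-6545 hold is triggered by fever or infection and ends when fever subsides. Neutrophil grade plays no part in the decision to restart, so limiting the row to Grade 3 has no evident purpose. The limit does have an effect. A subject with the same fever and a lower neutrophil count is routed to a line that asks for nothing on H3B-6545. A site that follows the table literally keeps dosing H3B-6545 through the worse event. The instruction stays in force for anyone on treatment, and Protocol 9.1.3 lets subjects continue into the Extension Phase.

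The secondary point concerns the count behind the MTD and behind the dose levels opened to intrasubject escalation. If no anemia can be a DLT, a subject with drug-related Grade 4 anemia and no other qualifying event enters that count as DLT-free.

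**Working it through.** **Febrile neutropenia.** No arithmetic applies, so the rows are set side by side.

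| Event | Palbociclib (Table 5) | H3B-6545 (Table 5) | DLT (Table 4) |
|---|---|---|---|
| Grade 3 neutropenia with fever | withhold, then lower | hold until fever subsides, same dose | yes |
| Grade 4 neutropenia with fever | withhold, then lower (general Grade 4 line) | no adjustment needed | yes |

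Table 4 equates Grade 2 or better with ANC of at least 1×10⁹/L. Its febrile criterion, ANC below that value, therefore covers Grade 3 and worse. For palbociclib the split in Table 5 changes nothing. Only the H3B-6545 column differs, and it differs in the wrong direction.

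For scale, Protocol 9.5 quotes febrile neutropenia in 1.8% of patients across palbociclib studies. With 12 to 24 escalation subjects that is 12 × 0.018 = 0.2 to 24 × 0.018 = 0.4 expected subjects, of whom Grade 4 would be a part. This is not a bound, because it is not the combination and the Table 5 row also covers infection.

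**Anemia.** Each possible route in Table 4 is closed:

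- The hematology row names only neutropenia and thrombocytopenia.
- The catch-all row and the dose-loss criterion exclude hematologic events.
- Table 7 classes hemoglobin under hematology, so the biochemistry row does not catch it.
- A subject who loses more than 25% of therapy because of toxicity remains evaluable (Protocol 9.1). She is not replaced and stays in the denominator.

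The escalate/stop outcome changes in two situations: 1 other DLT plus at least 1 Grade 4 anemia in another subject, or no other DLT plus at least 2 Grade 4 anemias.

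The documents give no rate for the combination. In Table 1 of Protocol 7.2.1, Grade 4 anemia is 0 in both groups (N=29 and N=21). For 0 of 50, the one-sided 95% upper bound is 1 − 0.05^(1/50) = 5.8%, and the two-sided one is 1 − 0.025^(1/50) = 7.1%. Both are any-cause and without palbociclib.

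Let b be the rate of DLTs already listed and a the rate of drug-related Grade 4 anemia, both assumed, and independent of each other. Then

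P(escalate) = P(Bin(6, q) ≤ 1), with q = b as written and q = b + (1 − b)a if the anemia counted.

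| b | a = 0 | a = 1% | a = 2% | a = 5% |
|---|---|---|---|---|
| 10% | 0.8857 | 0.8676 | 0.8487 | 0.7882 |
| 15% | 0.7765 | 0.7564 | 0.7360 | 0.6738 |
| 20% | 0.6554 | 0.6357 | 0.6161 | 0.5578 |

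The differences from the first column are 1.8 to 2.0 points at 1%, 3.7 to 4.1 at 2%, and 9.8 to 10.3 at 5%. If a instead means anemia in subjects with no other DLT, so that q = b + a, they are 2.0 to 2.5, 4.1 to 4.9 and 10.9 to 12.1.

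Both situations contribute. At b = 10% and a = 5% under independence, the first gives 6 × 0.1 × 0.9⁵ × (1 − 0.95⁵) = 0.080. The second gives 0.9⁶ × (1 − 0.95⁶ − 6 × 0.05 × 0.95⁵) = 0.017. The sum is 0.098, in line with the table.

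**The case against.** On the febrile row, Tables 5 and 6 are recommendations, clinical judgment governs, and Protocol 9.5 says that severe reactions may call for interrupting either drug. Stating that no adjustment is required does not forbid a hold. Amendment 3 explains the H3B-6545 column by saying that hematologic toxicity is not predicted with this drug. All of this is true and softens the rule. It does not explain a hold for febrile Grade 3 and none for febrile Grade 4. Table 6 is no substitute either: its general line concerns non-hematologic events and applies to Grade 3 or 4 only when they persist despite optimal care. A reader might infer that the protocol bars holding H3B-6545 in febrile Grade 4 neutropenia. The text does not say that.

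On anemia, the objection is stronger. A DLT list asks whether the combination is tolerable, and a dose-modification table advises on each drug. They need not mirror each other, so a difference between Tables 4 and 5 is not in itself an error. Leaving anemia out could be deliberate, since hemoglobin at entry may have been transfused and transfusion is allowed on study. The Safety Review Committee sees all safety data and sets the RP2D on an integrated evaluation, so the event is not hidden from it. SAP 3.2 says that no expansion subjects will be enrolled, and Amendment 4 says that further development is not planned. Escalation is therefore probably complete or nearly so. These arguments stand, and they reduce the anemia point to a conditional suggestion.

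**Conclusion.** The febrile row of Table 5 is a drafting defect in the current text: the more severe event receives the weaker written H3B-6545 action. Its frequency on the combination is unknown, and the number of subjects affected is probably small. It still merits correction, because it is a dosing instruction that applies now.

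That Table 4 has no route for anemia is also correct. Its effect is unknown and probably small. The 10-to-12-point figures need an assumed 5% rate, close to the upper bound from zero events in 50. They also treat the DLT count as the only input to the decision. A reader might infer that the MTD has been set too high. The documents do not support that: they report no Grade 4 anemia on the combination and no cohort result that would have changed.

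**What to change.** In Table 5, change the grade in the febrile neutropenia row label from 3 to 3 or 4 and leave the rest of the row as it is. Apply this to everyone still on treatment, including the Extension Phase. Palbociclib handling does not change in substance. The cost is one label and a short H3B-6545 hold, with restart at the same dose, for a few subjects.

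Only if a cohort is still to be assessed, the sponsor should consider adding drug-related Grade 4 anemia to the hematology row of Table 4 and its synopsis copy. Completed cohorts should not be rescored. No new assessments are needed, because Table 8 already schedules blood counts at the visits in the DLT window. The downside is that a lower dose could be declared the MTD. If no cohort remains, this change has no prospective effect and can be left out.
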